4.5 Treatment Assignment Procedures

4.5.1 *Randomization Procedures*

Eligible, consenting patients will be randomly allocated (1:1) to receive either CI or LPF using block randomization to ensure equal group sizes. Allocation will be determined in advance using a computer-based random number generator and stratified by primary joint type (MCP or PIP). We will use central randomization via a web-based system generated by the Biostatistics Unit at St Joseph's Healthcare—Hamilton. The randomization will be blocked within strata using randomly permuted blocks of various sizes. Approximately 2-3 months prior to their procedure, eligible, consenting patients will be randomized to one of the 2 treatments.

4.5.2 *Masking Procedures*

Blinding of patient and surgeon will not be possible. No or very minor scar is expected from collagenase injections. For palmar fasciectomy however, a noticeable scar is expected. As such, the patients will know which procedure they received. Outcome assessors will be hand occupational therapists or physiotherapists who will perform the goniometric measurements. Although they cannot be blinded for the same reason, they nevertheless work independent of the surgeon and therefore the risk of bias in the measurements will be mitigated. The statistician for the study however, can be blinded as he will be unaware of group allocation (Study A vs Study B).

As the palmar fasciectomy can be performed some weeks later there is a risk of cross-over but this can be avoided by obtaining the consent for palmar fasciectomy in the same clinic visit as the randomization.

4.6 Subject Withdrawal

Participants will be able to withdraw from the study at any point and for any reason, and without stating a reason. A 'consent to withdraw' with the permission to use/not use patient information will be signed by the patient. The reason for withdrawal will be documented and may include any of the following reasons: voluntary withdrawal, non-compliant patient, unable to contact patient (lost-to-follow-up), medical contraindication, adverse event(s), patient deceased, etc. In case of written withdrawal of consent for follow-up visits, and unless otherwise stated by the patient in the informed consent form, investigators will be encouraged to get information from the general practitioner, any other physician, or other medical-care provider, in order to follow the medical status of the patients (especially if they withdraw their consent after having experienced an AE/SAE). Investigators will also be expected to try as much as possible to re-contact those patients at the end of the trial, in order to obtain at least their vital status (dead or alive), as well as their health status (recurrence), and thus avoid lost to follow-up. For patients considered lost to follow-up, the CRF must be completed up to the last visit performed.

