6 STUDY PROCEDURES /EVALUATIONS

6.1 Schedule of Study Procedures

Patients referred to the recruiting surgeons will be screened for eligibility during their initial consultation. Patients who meet the inclusion criteria with no exclusion criteria present will be invited to join the trial and asked to provide written informed consent. Patients will be randomized after eligibility has been confirmed; it is expected that their procedure will occur 2-3 months after randomization. For the CI group, collagenase will be ordered and the procedure scheduled for as soon as possible following randomization. For the LPF group, the procedure will be done sometime in the ensuing weeks, as the procedure needs to be booked by the participating surgeon's office with the OR of the appropriate hospital. Approximately 1 week prior to their scheduled procedure, eligible, consenting patients will have their baseline data collected.

Surgeons may maintain their standard care for follow-up to patients. All patients will be seen for their study-specific follow-up visits at 1, 3, 6, and 12 months after their procedure. Best efforts will be made to coordinate routine patient care with study follow-up visits. Patients will be encouraged to contact their surgeon's office if they have any complications, questions, or concerns. If they are experiencing difficulties outside of regular hours, they will return to the emergency room of their surgeon's hospital. Patients will be asked at their follow-up visits if they have seen a physician not associated with the trial regarding their affected hand, and if so, the record will be obtained. If a patient is unable to return for follow up, copies of the quality of life questionnaires will be mailed to the patients. Reminder telephone calls will also be made to help ensure complete follow up.

If any unscheduled visits occur, the number of visits will be recorded in the patient's study diary. If occupational or physiotherapists are required to administer treatment, this information will also be recorded in the patient's study chart and in the study diary.

Additional visits for each of the study groups may occur as follows:

Collagenase Injection Group:

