8 STATISTICAL CONSIDERATIONS

8.1 General

Analysis of baseline characteristics will be performed using descriptive statistics reported by group as mean (standard deviation [SD]) or median (first quartile, third

quartile) for continuous variables and count (percent) for categorical variables. All analyses of primary and secondary outcomes will follow the intention-to-treat principles. We will use multiple imputation to handle missing data [25]. The results for comparisons between groups will be presented as mean difference (for continuous outcomes) and relative risk (for binary outcomes), corresponding 95% confidence intervals and associated p-values. P-values will be reported to four decimal places with p-values less than 0.001 reported as $p < 0.001$. All analyses will be performed using SAS software version 9.4 (Cary, NC, USA).

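### Randomized patients who never have a procedure have no scheduled 12-month MHQ, so the intention-to-treat analysis would rest on an imputation with almost nothing behind it

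*Combined protocol and SAP*

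**What the plan says.** **Withdrawal (4.6).** Patients may leave at any time. The plan asks sites to record why and offers examples, without requiring that anyone be withdrawn: "voluntary withdrawal, non-compliant patient, unable to contact patient (lost-to-follow-up), medical contraindication, adverse event(s), patient deceased, etc". Non-compliance, contraindication and adverse events are treatment events, yet they stand beside death and loss of contact as reasons for leaving the study. For patients who withdraw consent to follow-up visits, investigators are asked to re-contact them when the trial closes "in order to obtain at least their vital status (dead or alive), as well as their health status (recurrence), and thus avoid lost to follow-up". The MHQ is not named there.

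**Timing.** Section 4.5.1: "Approximately 2-3 months prior to their procedure, eligible, consenting patients will be randomized to one of the 2 treatments". Section 6.1: "Approximately 1 week prior to their scheduled procedure, eligible, consenting patients will have their baseline data collected", and "All patients will be seen for their study-specific follow-up visits at 1, 3, 6, and 12 months after their procedure". Sections 6.2 and 6.3 and the Appendix use the same procedure-based schedule for baseline and follow-up.

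**Analysis (8.1).** "All analyses of primary and secondary outcomes will follow the intention-to-treat principles". Missing data are to be handled by multiple imputation. No imputation model, missingness assumption or sensitivity analysis is given.

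**Endpoint.** Sections 2.1 and 8.2 date the primary MHQ 12 months from randomization, and 2.1 adjusts for a score taken before randomization. Section 3.2 dates it one year from treatment.

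**The concern.** An intention-to-treat analysis needs the outcome from everyone randomized, whatever treatment they received. Here the collection of the outcome depends on the procedure taking place. Two to three months is long enough for some patients to change their mind, become unfit for surgery or lose drug coverage. Because the trial is open-label, they know their arm while they wait.

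The reasons for a cancelled procedure need not be the same in the two arms. Section 6.1 schedules collagenase as soon as possible after randomization, while fasciectomy waits for an operating-room booking. Collagenase depends on insurance coverage (4.2). Missing MHQ scores could therefore be related to arm, and plausibly to outcome, and they cannot be recovered afterwards.

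**Working it through.** **1. What exists for a randomized patient who never has a procedure**

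| Item | When the plan collects it | Available without a procedure? |
|---|---|---|
| Arm and joint stratum | Randomization, 2-3 months before the procedure (4.5.1, 6.1) | Yes |
| Baseline MHQ, other questionnaires, range of motion, demographics | About 1 week before the scheduled procedure (6.1, 6.2) | Only if the cancellation comes after this visit |
| MHQ at 1, 3, 6 and 12 months | Counted from the procedure (6.1, 6.3, Appendix) | No due date exists |
| End-of-trial re-contact | For those who withdrew consent to visits (4.6) | At least vital status and recurrence; MHQ not named |

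If the cancellation comes more than about a week ahead, the imputation model has arm, joint stratum and whatever was noted at screening. The 12-month scores it can learn from belong to patients who had a procedure, so it would in effect assign treated outcomes to untreated patients.

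**2. The planned sample size**

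Inputs from 8.2: difference 8.7, SD 15.5, alpha 0.05 (read as two-sided), power 0.80 (printed there as beta), baseline correlation 0, loss 20%.

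n per arm = 2 × [(1.960 + 0.842) × 15.5 / 8.7]² = 49.83, rounded up to 50. One extra patient per arm in the ANCOVA formula, or solving with the t distribution (50.8), gives 51, so 102 in total. Then 102 / 0.80 = 127.5, rounded up to 128. Both stated figures reproduce. A one-sided test would give 40 per arm and does not match. Power at 51 per arm is 0.809 by the normal approximation. There is no separate allowance for untreated patients.

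**3. Possible error in one arm's mean**

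Let f be the fraction of an arm without a procedure and D the points by which their 12-month MHQ falls below that of treated patients. The mean over all randomized patients is (treated mean − f × D). Imputing them as treated returns the treated mean, so the error is f × D. Neither f nor D is in the documents; the ranges are assumed.

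| f | Patients of 64 | D = 5 | D = 10 | D = 15 |
|---|---|---|---|---|
| 5% | 3.2 | 0.25 | 0.50 | 0.75 |
| 10% | 6.4 | 0.50 | 1.00 | 1.50 |
| 15% | 9.6 | 0.75 | 1.50 | 2.25 |
| 20% | 12.8 | 1.00 | 2.00 | 3.00 |

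Against 8.7 points the table runs from 0.25 / 8.7 = 3% to 3.0 / 8.7 = 34%. The error in the treatment difference is f₁D₁ − f₂D₂, which is zero if both arms lose similar patients at the same rate.

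**4. Precision**

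Suppose a fraction f of each arm has no MHQ on top of the 20% loss. Evaluable patients per arm are 64 × (0.80 − f) = 48.0, 44.8, 41.6 and 38.4 for f = 5, 10, 15 and 20%. Power for 8.7 points is then 0.785, 0.757, 0.726 and 0.691. If the untreated patients already fall within the 20%, there is no further loss.

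**The case against.** A reader might infer that the plan removes non-compliant or untreated patients from the analysis, so that the primary comparison becomes one of patients who received a procedure. The documents do not support this. No section excludes them, and 8.1 keeps them in through intention-to-treat and multiple imputation. The list in 4.6 records reasons that may be given; it does not require anyone to be withdrawn. The vital-status sentence concerns patients who withdrew consent to visits, and it sets a minimum.

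Other text also narrows the problem:

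- Section 4.4 promises every reasonable effort to follow all participants to the end of the trial, with questionnaires by mail or email for those who cannot or will not attend.
- Section 4.2 excludes, at entry, patients who are unfit for surgery, have a treatment preference or lack collagenase coverage.
- Section 4.5.2 foresees cross-over and tries to limit it through the timing of consent. Patients who switch arms do have a procedure date and can be followed.
- Patients with an adverse event after the procedure, or found unfit on the day, would normally have a baseline MHQ.
- The Appendix places randomization in the column headed one week before the procedure. If that were the practice, the waiting period would largely disappear. It conflicts with 4.5.1 and 6.1, and with 4.5.2, which expects fasciectomy some weeks later.

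All of this stands, and it limits the point to patients who have no procedure at all. It does not close that gap. The entry criteria do not cover changes during the wait. The promise in 4.4 sets no date for an MHQ when no procedure has taken place, and no section says how untreated patients are followed.

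**Conclusion.** The point holds in this limited form. The plan does not distinguish a treatment deviation from study withdrawal, and it has no MHQ schedule for a randomized patient without a procedure. For those patients the declared intention-to-treat result would depend on an unspecified imputation drawn from treated patients.

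The size cannot be determined from the documents. An error of 0.25-3.0 points in one arm requires the assumed non-receipt of 5-20% and an assumed deficit of 5-15 points, where 15 points is about one planning SD. It carries fully into the treatment difference only if non-receipt is confined to one arm. These figures show what is possible; they do not show that bias is likely. The change is still worth making, because it is cheap and an MHQ that was never collected cannot be reconstructed.

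**What to change.** - **4.6:** State that not receiving, refusing, switching or stopping the assigned treatment, for whatever reason, is recorded as a treatment deviation and not as study withdrawal. Only withdrawal of consent, death or loss of contact ends follow-up.
- **6.1:** Collect the MHQ from every randomized patient whether or not a procedure takes place, by mail or email where needed. Sections 4.4 and 6.1 already provide for remote questionnaires.
- **Baseline:** Collect the baseline MHQ before randomization, as 2.1 already implies. Every patient then has a score for the covariate adjustment and for imputation.
- **Time origin:** Reconcile 2.1 and 8.2 (randomization) with 3.2 (treatment), and date the 12-month MHQ of patients without a procedure from randomization. A nominal procedure date would be an alternative, but it adds a third origin to two that already conflict. Correct the Appendix column for randomization at the same time.
- **8.1:** For scores that are still missing, name the imputation variables and a sensitivity analysis.

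The cost is protocol wording, an earlier baseline questionnaire and a few mailed forms. If treated patients are timed from the procedure, their 12-month score falls about 14-15 months after randomization (12 plus 2-3), so the score of an untreated patient at 12 months is only approximately comparable.

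The change does not buy power. If untreated patients are observed and dilute the difference to 8.7 × (1 − f), power with 51 evaluable per arm is 0.768, 0.723, 0.673 and 0.621 for f = 5, 10, 15 and 20%. The gain is that the estimate describes the patients who were randomized.

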5 STUDY INTERVENTIONS

5.1 Collagenase Injection (CI) Group

This procedure will be performed either in a minor procedure room or the hand clinic as per surgeon's routine practice. Collagenase will be administered with or without local anesthesia. As this is a pragmatic study we may inject more than one digit at a time just as we operate on more than one digit at a time. A recently published study by Gaston et al confirmed that two concurrent injections of CI to 2 affected joints in the same hand are generally well tolerated and the frequency of most AEs is similar to those reported in studies that use single sequential injections [19].

The patient's affected hand will be prepped with antiseptic solution. Using a hubless syringe with 0.01 mL graduations and a permanently fixed 26- or 27-gauge $\frac{1}{2}$ inch needle the required amount of reconstituted collagenase clostridium histolyticum will be withdrawn as follows: a) Cord affecting an MP joint, withdraw 0.25 mL of the reconstituted solution; b) Cord affecting a PIP joint: withdraw 0.20 mL of the reconstituted solution per published guidelines.

While applying tension to the cord in the hand to be treated, the needle will be placed into the cord while carefully ensuring that the tip stays within the cord and does not pass through the cord. After confirming the needle is placed correctly in the cord,

approximately one-third of the dose is injected. The needle tip is then withdrawn from the cord and repositioned in a slightly more distal location to the initial injection in the cord (approximately 2 to 3 mm) and another one-third of the dose is injected. Again, the needle tip is withdrawn from the cord and repositioned proximal to the initial injection (approximately 2 to 3 mm) and the final portion of the dose injected into the cord. When injecting a cord affecting the PIP joint of the fifth finger, the needle insertion should not be more than 2 to 3 mm in depth and injecting more than 4 mm distal to the palmar digital crease should be avoided.

After the injections are completed, the patient's treated hand will be wrapped with a soft, bulky gauze dressing and kept elevated for the remainder of the day. The patient will return to the surgeon's office/clinic 1-7 days post-injection to assess if the contracture has resolved. If a contracture remains, a passive finger extension procedure, with or without local anesthesia as determined by the surgeon, will be undertaken in an attempt to disrupt the cord. If residual contracture remains the patient will return for a 30-day follow-up when the cord may be reinjected and the finger extension procedure repeated.

5.2 Limited Palmar Fasciectomy (LPF) Group

The Dupuytren's cord will be excised under local anesthesia in a minor procedure room setting or main operating room under local or general anesthetic depending on the complexity of the disease and the surgeon's routine. As this is a pragmatic study we will be comparing CI (novel intervention) to LPF as it is actually presently performed in all settings academic or community (local in minor room or general/local anesthetic in the main operating room). The procedure will be performed according to the operating surgeon's preferred technique i.e. zig-zag Brunner incision or straight incision with z-plasty closure of the skin. Loupe magnification will be used in surgery to identify and protect the digital neurovascular bundles. The diseased Dupuytren's fascia (cords) causing the contracture will be excised. Contracted ligaments at the PIP joints may be released by passive stretching or with knife intraoperatively. A plaster splint will be applied at the discretion of the surgeon. Patients will be discharged home the same day as their surgery and will return within 1 week for assessment.

5.3 Concomitant Medications/Treatments

Medicines for pain control will be prescribed at the discretion of the operating surgeon.

5.4 Procedures for Training of Clinicians on the Interventions

As CI is the “novel” intervention in this RCT, we need to consider the learning curve. Participating surgeons will be expected to review the detailed description of the technique, by viewing the provided learning video (http://www.xiaflexrems.com/video/dupuytren/Xiaflex_REMS.html) and have performed at least 10 CI injections with successful correction of the extension deficit (less than 5°) without serious complication before they begin the enrollment in the study.

6 STUDY PROCEDURES /EVALUATIONS

6.1 Schedule of Study Procedures

Patients referred to the recruiting surgeons will be screened for eligibility during their initial consultation. Patients who meet the inclusion criteria with no exclusion criteria present will be invited to join the trial and asked to provide written informed consent. Patients will be randomized after eligibility has been confirmed; it is expected that their procedure will occur 2-3 months after randomization. For the CI group, collagenase will be ordered and the procedure scheduled for as soon as possible following randomization. For the LPF group, the procedure will be done sometime in the ensuing weeks, as the procedure needs to be booked by the participating surgeon's office with the OR of the appropriate hospital. Approximately 1 week prior to their scheduled procedure, eligible, consenting patients will have their baseline data collected.

Surgeons may maintain their standard care for follow-up to patients. All patients will be seen for their study-specific follow-up visits at 1, 3, 6, and 12 months after their procedure. Best efforts will be made to coordinate routine patient care with study follow-up visits. Patients will be encouraged to contact their surgeon's office if they have any complications, questions, or concerns. If they are experiencing difficulties outside of regular hours, they will return to the emergency room of their surgeon's hospital. Patients will be asked at their follow-up visits if they have seen a physician not associated with the trial regarding their affected hand, and if so, the record will be obtained. If a patient is unable to return for follow up, copies of the quality of life questionnaires will be mailed to the patients. Reminder telephone calls will also be made to help ensure complete follow up.

If any unscheduled visits occur, the number of visits will be recorded in the patient's study diary. If occupational or physiotherapists are required to administer treatment, this information will also be recorded in the patient's study chart and in the study diary.

Additional visits for each of the study groups may occur as follows:

Collagenase Injection Group:

Patients in the CI group will return to the surgeon's office within 1-7 days after receiving their injection to determine if the contracture has resolved. If a contracture remains, a passive finger extension procedure will be undertaken in an attempt to disrupt the cord. If residual contracture remains the patient will return for a 30-day follow-up when the cord may be reinjected and finger extension procedure repeated.

Limited Palmar Fasciectomy Group:

Patients in the LPF group will return to the surgeon's office 1 week following their procedure.

The schedule of study procedures is presented in the Appendix.

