2 STUDY OBJECTIVES

2.1 Primary Objective

The primary objective of this study is to compare the clinical effectiveness of collagenase injections (CI) versus limited palmar fasciectomy (LPF) as measured by the 12 month post-randomization Michigan Hand Questionnaire (MHQ) after adjusting for the pre-randomization MHQ score.

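### Section 2.1 anchors the primary MHQ comparison to randomization, but the text schedule anchors both MHQ assessments to the procedure, and the Appendix conflicts with the text on when randomization occurs

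*Combined protocol and SAP*

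**What the plan says.** **Primary comparison.** Section 2.1 compares the arms on the "12 month post-randomization Michigan Hand Questionnaire (MHQ) after adjusting for the pre-randomization MHQ score". Section 8.2 also counts the 12 months from randomization, but calls the covariate the baseline MHQ. Section 3.2 puts the primary outcome one year after treatment.

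**Randomization.** Section 4.5.1: "Approximately 2-3 months prior to their procedure, eligible, consenting patients will be randomized to one of the 2 treatments". Section 6.1 agrees: "it is expected that their procedure will occur 2-3 months after randomization". Section 6.1 then separates the arms. For CI, "collagenase will be ordered and the procedure scheduled for as soon as possible following randomization"; for LPF, the date depends on operating room booking.

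**MHQ assessments.** Section 6.1: "Approximately 1 week prior to their scheduled procedure, eligible, consenting patients will have their baseline data collected". Section 6.2 lists the MHQ among the questionnaires given at that visit. Sections 6.1 and 6.3 set follow-up at 1, 3, 6 and 12 months after the procedure.

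**Knowledge of allocation.** Section 4.5.2: "Blinding of patient and surgeon will not be possible". It adds: "As the palmar fasciectomy can be performed some weeks later there is a risk of cross-over", to be avoided by "obtaining the consent for palmar fasciectomy in the same clinic visit as the randomization". LPF patients would therefore know their allocation from that visit.

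**Appendix.** Section 6.1 refers to the Appendix for the schedule. It marks randomization and the first HRQL questionnaires in the same -1 week column and does not say which comes first.

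**The concern.** A primary objective should name measurements that the schedule produces. Here the objective counts from randomization and the visits count from the procedure, with a planned wait of 2-3 months between the two. An analyst working from 2.1 and an analyst working from 3.2 and 6.3 would describe different primary time points, and 2.1 also describes a covariate that the text schedule does not collect.

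Two consequences go beyond wording. First, the covariate is a self-report from unblinded patients. If it is given after they learn their allocation, it may be affected by that knowledge, and adjusting for it could then move the estimated treatment effect. Second, follow-up that starts at the procedure gives no date for the final MHQ of a randomized patient who is never treated, although Section 8.1 plans intention-to-treat analysis.

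**Working it through.** **1. The plan's own sample size.** Inputs from Section 8.2: difference 8.7, SD 15.5 (midpoint of 15.0 and 16.0), alpha 0.05 (taken as two-sided), power 0.80, correlation 0.0, loss 20%.

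- Normal approximation: n per arm = 2 × [15.5 × (1.960 + 0.842) / 8.7]² = 49.8.
- The t-test version gives 50.8, so 51 per arm and 102 in total.
- The covariance factor is 1 − 0.0² = 1, so the covariate earns no reduction.
- Losses: 102 / 0.80 = 127.5, so 128.

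Both stated figures reproduce. Since the covariate earns no credit, they do not depend on which MHQ is used as baseline.

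**2. Timing.** One month = 365.25 / 12 / 7 = 4.35 weeks. Let w be the wait from randomization to procedure.

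| Quantity | Formula | w = 2 months | w = 3 months |
|---|---|---|---|
| First MHQ, weeks after randomization | 4.35w − 1 | 7.7 | 12.0 |
| Last MHQ, months after randomization | 12 + w | 14 | 15 |
| 12 months after randomization, in months after procedure | 12 − w | 10 | 9 |

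The third row lies between the 6- and 12-month visits, where no MHQ is scheduled. The intervals are approximate, and the CI wait may be shorter because Section 6.1 books CI as early as possible.

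Read alone, the Appendix has w of about 1 week. The last MHQ is then 12 + 1/4.35 = 12.2 months after randomization, close to 2.1, and an MHQ before allocation would be possible. Against 4.5.1 and 6.1, the Appendix randomization time differs by the same 7.7 to 12.0 weeks.

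**3. Which places agree.**

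- Procedure-anchored outcome: 3.2, 6.1, 6.3, the Appendix follow-up columns, and the 12-month post-operative source of the SD of 16.0 in 8.2.
- Randomization-anchored outcome: 2.1 and the outcome label in 8.2.
- Covariate at about −1 week: 6.1, 6.2, the Appendix, and the one-week pre-operative source of the SD of 15.0. Section 8.2 adjusts for baseline MHQ, and 6.2 defines the baseline visit.
- Covariate before randomization: 2.1 only.
- Randomization 2-3 months before the procedure: 4.5.1 and 6.1. At −1 week: the Appendix.

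**4. Power of an unadjusted comparison.** Two-sided t-test, 51 per arm, difference 8.7: 0.802 at SD 15.5 and 0.776 at SD 16, the 12-month value in 8.2.

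**The case against.** The strongest reply is that the fault lies mostly in labels. The operational sections agree with each other. Section 8.2 names the baseline MHQ, uses a sample-size method for analysis of covariance and states its linearity and parallel-slope assumptions, and 6.2 says when baseline is. So the covariate can be identified, and only 2.1 departs from it. Under the text schedule the data will contain one candidate comparison at 12 months. A baseline taken close to treatment is also defensible in a gradually progressive condition with a wait of 2-3 months. All of this stands, and it rules out the reading that the plan leaves the primary analysis undefined or impossible to compute.

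A reader might also infer that the treatment estimate is biased by a known amount or in a known direction. The documents do not support that. The movement depends on how far allocation shifts the −1 week score, which they do not give, and on the correlation with the 12-month score, which 8.2 sets at 0.0. At that value the movement is zero. Exclusion 6, which removes patients with a treatment preference, may limit any shift, although it does not measure it.

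Nor can one say that missing baselines are ignored: Section 8.1 plans multiple imputation, which covers them in principle. Imputation does not, however, set the time at which a never-treated patient's final MHQ is due.

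What survives the objection is that the comparison the sections agree on is not the comparison the primary objective states, and that the Appendix contradicts the text on randomization.

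**Conclusion.** The contradiction is in the current text and should be corrected before analysis. Under 4.5.1 and 6.1-6.3, neither MHQ named in 2.1 is collected. The first is roughly 8-12 weeks after randomization instead of before it, and the last is roughly 14-15 months after randomization instead of 12. The outliers are 2.1, the outcome label in 8.2 and the randomization time in the Appendix. These sizes rest on the planned wait of 2-3 months, which may be shorter for CI.

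The sample size of 102/128 is unaffected. That the covariate may be affected by knowledge of allocation is a possibility created by the schedule, not a demonstrated bias. The case for correction rests on the contradiction alone.

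**What to change.** 1. **One time origin.** Amend 2.1 and 8.2 to 12 months after the procedure, matching 3.2 and 6.3. Report days from randomization to procedure by arm. State when never-treated patients give the final MHQ; the choice is the sponsor's.
2. **Appendix.** Reconcile it with 4.5.1 and 6.1 on when randomization occurs, and state the order of randomization and the first MHQ.
3. **Patients not yet randomized.** Collect the MHQ at the consent visit, before the allocation is released, and use it as the covariate, as 2.1 already says. Keep the −1 week MHQ as well.
4. **Patients already randomized.** Name the covariate in 2.1 as the pre-procedure, post-allocation MHQ, and add an unadjusted sensitivity analysis. Its power is about 78-80% at 51 per arm (SD 16 to 15.5).
5. If both groups of patients exist, state which covariate applies to whom. Fix all these choices before database lock.

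**Cost.** A protocol amendment with REB review and no added patients. Item 3 adds about 15 minutes at an existing visit (6.4.1). An MHQ taken 8-12 weeks earlier may correlate somewhat less with the 12-month score. If the correlation fell from 0.5 to 0.3 (both assumed), power at SD 15.5 and 51 per arm would fall from 90% to 84%, still above the planned 80%. The 4-year follow-up in 3.3(h) and the telephone consent in 9.3 suggest that enrolment may be over. In that case item 3 applies to nobody, and the remaining items are corrections to the text plus one extra analysis.
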